### 6.3.1. Period 1 - data collection at PACU arrival

Immediately after patient arrival in the PACU and as soon as clinically adequate (basic monitoring and oxygen therapy in place) the anesthesiologist assigned to the PACU (who was not involved in the anesthetic procedure) will collect demographic data (gender, age, weight, height), vital signs (heart rate, blood pressure, oxygen saturation and temperature). Neuromuscular blockade (TOF Ratio) will be measured. Clinical history, co-morbidities, surgical diagnosis, ASA classification and perioperative medication data (dosage and last administration time) will be collected as well.

As this is an observational study, intra-operative monitoring of neuromuscular blockade will not be mandatory by protocol and will be left at the discretion of the anesthesiologist as according to the clinical practice. Only information about whether this evaluation was performed or not, and if yes if it was used quantitative or qualitative methods, will be collected in the CRF.

#### Neuromuscular blockade evaluation

Neuromuscular blockade will be evaluated using a quantitative method. Three consecutive TOF stimulations will be applied. In case these 3 measures differ more than 20%, another

sequence of 3 consecutive TOF measurements will be considered. If after the 2nd sequence the 3 consecutive TOF measurements still differ more than 20% between the maximum and the minimum the patient will be excluded.

#### Residual neuromuscular blockade definition

Residual neuromuscular blockade will be defined by a TOF ratio < 0.9.

Patients will be stratified as follow:

TOF ratio  $\geq$  0.9 – Absence of Residual Neuromuscular Blockade

TOF ratio < 0.9 – Presence of Residual Neuromuscular Blockade

TOF ratio < 0.7 – Presence of severe Residual Neuromuscular Blockade

### 6.3.2. Period 2 - Discharge data collection

Hospital Patient Discharge Data will be collected for each subject. The occurrence of SAEs and AEs will be recorded as well as the final outcome.

### 6.3.3. Other considerations

This study will reflect real life clinical practice. The anesthetic technique in terms of drugs and type of monitoring used will be of entire responsibility of the anesthesiologist.

All study activities will be consistent with EU directive 2001/20/EC section for noninterventional studies :

- NMBAs and reversal agents' (as well as all drugs which will be used during the anesthesia) administration will be done in accordance with routine anesthesiology practice and labeling of these medicine products;
- No further interventional means, methods or procedures, are scheduled for subjects, which would otherwise not be applied;
- Furthermore, there will be no additional visits to the hospital or a mandatory visit schedule, deviating from daily clinical practice.

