# 1.1. Study Flow Chart

|  | Pre-
surgery           | Post-surgery                       |  |
|--|---------------------------|------------------------------------|--|
| Procedures   | At
Anesthetic
visit | Period 1
At PACU arrival | Period 2
At hospital discharge |
| Written informed consent   | x                         |                                    |  |
| Inclusion/exclusion criteria   | x                         | x                                  |  |
| Patient number   |                           | x                                  |  |
| Vital signs: arterial blood, pressure,
heart rate, temperature and oxygen
saturation |                           | x                                  |  |
| Neuromuscular blockade assessment
(TOF ratio measurements)                              |                           | x                                  |  |
| Demographic data (gender, age,
weight, height)  |                           | x                                  |  |
| Clinical history   |                           | x                                  |  |
| Co-morbidities   |                           | x                                  |  |
| Information about operating room   |                           | x                                  |  |
| Surgical diagnostic  |                           | x                                  |  |
| ASA status   |                           | х                                  |  |
| Medication: NMBA, NMBA reversal agents, volatile anesthetics, hypnotics, opioids           |                           | x                                  |  |
| Dates: discharge/death   |                           | x                                  |  |
| Adverse events   |                           |                                    | x  |
| Final outcome: discharge/death   |                           |                                    | x  |

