### 7.6.2. Variables and Statistical Methods

#### Variables/Time Points of Interest

- Demographic/anthropometric information (i.e: age, sex, height and weight)
- Clinical history
- Co-morbidities
- Vital signs (i.e.temperature, oxygen saturation, heart rate and arterial blood pressure)
- ASA classification
- Surgical diagnostic
- Anesthesia duration (time)
- Perioperative medication, its' dosages and last administration time (used during surgical procedure, including neuromuscular blocker and reversal agents)
- Time between date of surgery and date of discharge
- TOF ratio at PACU
- Adverse events
- Assessment if NMB monitoring in the OR during surgery was performed
- Final outcome (discharge or death).

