#### Secondary Variables and Exploratory Variables

Comparisons will be performed between TOF ratio <0.9, TOF ratio <0.7 at PACU, and the following variables:

- the use of reversal agents (neostigmine, sugammadex or none)
- NMB monitoring used intraoperatively and type of monitoring used
- o co-morbidities and ASA status

Statistical significance of the comparisons with TOF ratio <0.9 and TOF ratio <0.7 at PACU will be performed through Chi-square test or Fisher's Exact Test. In addition, relative risks and 95% CI for TOF ratio <0.7 and TOF ratio <0.9 at PACU will be performed for the comparisons. All tests will be performed considering a significance level of 0.05 (5%). Analysis will be performed using IBM SPSS Statistics.

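### The tests of reversal agent and monitoring treat patients as independent, although exposure is chosen by the anesthesiologist within about ten centers; error rates may exceed 5% and need a center-clustered analysis

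*Combined protocol and SAP*

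**What the plan says.** Two of the three secondary objectives (section 5.2) are associations: residual block with reversal agent (neostigmine, sugammadex or none), and residual block with intra-operative monitoring. Both exposures are left to the treating clinician. Section 6.3.3 states that "The anesthetic technique in terms of drugs and type of monitoring used will be of entire responsibility of the anesthesiologist", and section 6.3.1 that "intra-operative monitoring of neuromuscular blockade will not be mandatory by protocol and will be left at the discretion of the anesthesiologist".

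Section 6.1 plans 360 patients from about ten centers, with 30 to 40 per center.

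For the associations, section 7.6.2 (Secondary Variables and Exploratory Variables) says that significance "will be performed through Chi-square test or Fisher's Exact Test" and that "relative risks and 95% CI for TOF ratio <0.7 and TOF ratio <0.9 at PACU will be performed for the comparisons", all at the 0.05 level. No cluster term, robust variance, GEE or mixed model appears anywhere in the plan.

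On monitoring, section 6.3.1 limits the CRF record to whether it was done and, where it was, whether the method was quantitative or qualitative. The variable list in section 7.6.2 has "Assessment if NMB monitoring in the OR during surgery was performed" but neither an anesthesiologist code nor center. The flow chart (section 1.1) has an item "Information about operating room" whose content is not defined.

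**The concern.** An anesthesiologist, or a department, tends to treat its patients alike. Patients who share a practitioner or hospital may therefore share the exposure. They also share the rest of the technique, such as the blocking agent and its timing, which can affect the TOF ratio at PACU arrival. The Rationale (section 4) makes uneven practice plausible: teaching sessions were held in various hospitals, and sugammadex has displaced older agents in many cases but not all.

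When exposure and outcome are both correlated within the same groups, the data carry less information about the association than the patient count suggests. A chi-square test or an ordinary relative-risk interval does not allow for this. Its p-value is then too small and its interval too narrow. At stake is the reliability of any statement that reversal agent or monitoring is associated with residual block.

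**Working it through.** **The plan's own figure.** The only sizing, in section 7.1, is for the primary incidence: 26%, margin 5 points, 95% confidence, population 100,000.

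- n0 = 1.96² × 0.26 × 0.74 / 0.05² = 295.6.
- With finite population correction: 295.6 / (1 + 294.6/100,000) = 294.8, rounded up to 295. This reproduces the plan.
- For 20% loss, 295/0.8 = 369 and 295 × 1.2 = 354. The plan's figure of about 360 is within 3% of both.

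The primary calculation is not in dispute. No sample size is given for the associations.

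**Inputs for the check.** From the documents: 295 evaluable patients, 26% with TOF ratio below 0.9, about ten centers, alpha 0.05 (taken as two-sided). Assumed, because the documents are silent: half of patients exposed, the number of anesthesiologists, and the intra-cluster correlations (ICC) of exposure and outcome.

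**Formula.** With m patients per cluster and no true association, the variance is multiplied by about

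DE = 1 + (m − 1) × ICC(exposure) × ICC(outcome),

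and the true error of the nominal 5% test is about 2 × [1 − Φ(1.96/√DE)].

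Example with five anesthesiologists per center: m = 295/50 = 5.9 and DE = 1 + 4.9 × 0.5 × 0.1 = 1.245. Then 1.96/√1.245 = 1.757, and the error is 7.9%.

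**Results.** The simulated columns come from 10,000 beta-binomial runs per scenario. They give the error of the Pearson chi-square test and the coverage of the nominal 95% relative-risk interval.

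| Clusters | m | ICC exposure | ICC outcome | DE | Error, formula | Error, simulated | Coverage |
|---|---|---|---|---|---|---|---|
| 30 anesthesiologists | 9.8 | 0.2 | 0.05 | 1.09 | 6.0% | 5.6% | 94.7% |
| 30 anesthesiologists | 9.8 | 0.5 | 0.1 | 1.44 | 10.3% | 10.1% | 90.3% |
| 30 anesthesiologists | 9.8 | 0.8 | 0.2 | 2.41 | 20.7% | 20.4% | 80.2% |
| 50 anesthesiologists | 5.9 | 0.5 | 0.1 | 1.25 | 7.9% | 8.8% | 91.6% |
| 100 anesthesiologists | 2.95 | 0.5 | 0.1 | 1.10 | 6.1% | 5.8% | 94.5% |
| 180 anesthesiologists | 1.6 | 0.5 | 0.1 | 1.03 | 5.4% | 5.7% | 94.6% |
| 10 centers | 29.5 | 0.1 | 0.05 | 1.14 | 6.7% | 6.3% | 93.9% |
| 10 centers | 29.5 | 0.2 | 0.05 | 1.29 | 8.4% | 7.8% | 92.7% |
| 10 centers | 29.5 | 0.5 | 0.05 | 1.71 | 13.4% | 12.8% | 87.8% |

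With exposure ICC 0, the simulated error is 4.7% to 5.3%: no inflation.

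**Which level to cluster on.** These are further simulations of cluster-robust tests, with ten centers, about 300 patients and anesthesiologists nested in centers.

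- Correlation at anesthesiologist level only (0.5 exposure, 0.1 outcome): clustering on center with a t reference on 9 degrees of freedom gave an error of about 4% to 6%. Clustering on anesthesiologist gave 4.7% to 5.8%.
- Center correlation added (for example 0.2 and 0.05 on top of 0.5 and 0.1, or 0.3 and 0.05 on top of 0.2 and 0.05): clustering on anesthesiologist alone still rejected in about 6.7% to 9.6% of runs. Clustering on center gave 5.4% to 5.9%.

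**The case against.** The strongest reply is that the inflation is conditional and could be negligible. It needs positive correlation in both exposure and outcome, and several patients per cluster. Sites are hospitals with many general anesthetics (section 6.5), so 30 to 40 patients could be spread over 10 to 18 anesthesiologists. At 0.5 and 0.1 the anesthesiologist-level error is then only about 5.7% to 5.8%. This stands, and it is why the point says the tests may be too optimistic. A reader might infer that they certainly are; the documents supply none of the quantities needed to say so. The reply does not dispose of center-level clustering, which the design itself makes possible at about 30 patients per cluster.

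A reader might also infer that the problem cannot be repaired because the anesthesiologist is not recorded, or that it would persist within hospitals even if center were handled. Neither follows. A variance clustered on center allows any correlation within a center, including that due to its anesthesiologists, and the enrolling site should be recoverable. Persistence would be true of some other treatments of center, such as fixed effects alone. Nor do the documents show that no identifier is collected: the CRF is not among them and one flow-chart item is undefined. They show only that none is listed.

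Finally, these are secondary analyses in an observational study whose sample size was set for the primary incidence. That limits the stakes but does not make the tests valid.

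**Conclusion.** The planned tests and intervals for reversal agent and monitoring ignore clustering that the design makes plausible. If exposure and residual block are both positively correlated within center or anesthesiologist, they are anti-conservative. Under assumed correlations the true error of the nominal 5% test runs from about 5% (no exposure clustering) through about 6% to 13% in moderate scenarios. It reaches about 20%, with interval coverage near 80%, in an extreme one: three anesthesiologists per center, ICCs 0.8 and 0.2. Which of these applies cannot be told from the documents.

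The point leaves the primary sample-size calculation alone. It should also not be read as a remedy for confounding. An apparent drug or monitoring effect that really reflects the other habits of certain practitioners would remain after the standard errors are corrected.

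**What to change.** In section 7.6.2, obtain the relative risks, 95% intervals and p-values for reversal agent and monitoring from a log-link model (modified Poisson or GEE) with robust variance clustered on center. With only about ten clusters, specify a small-sample correction, for example a t reference with degrees of freedom equal to the number of centers minus one. Add center to the list of analysis variables. Keep the chi-square or Fisher tables as description.

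Optionally, add a coded, non-identifying anesthesiologist number to the CRF, so that clustering within centers can be described. The main correction does not depend on it. If such a code is already collected, state where.

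The cost is SAP wording, one optional CRF field and somewhat wider intervals for the secondary associations. No extra patients or procedures are needed. The report should say that the correction addresses precision and error rate, not confounding by practitioner.

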### 6.3.4. Study Schedule

The study schedule and activities are provided in the Study Flow Chart in Section 1.1.

## 6.4. Target Population

### 6.4.1. Subject Inclusion Criteria

To participate in this study subjects must meet the following criteria:

- 18 years of age or older;
- Informed consent signed;
- Admission for elective surgery;
- Administration of non-depolarizing NMBAs during surgery.

### 6.4.2. Subject Exclusion Criteria

Subjects will be excluded from this study if they do not fulfill the inclusion criteria or in case of:

- Admission for emergency surgery;
- Reoperation on the same hospital admission;
- More than 10 minutes elapsed between extubation and neuromuscular block monitoring at PACU.

### 6.4.3. Subject Discontinuation Criteria

A subject may discontinue the study at any time without having to state the reason. As this is an observational study, discontinuation from the study does not mean any change to the surgical, anesthesia or medical care procedures.

Additionally subject participation must be terminated during the study for any of the following reasons:

• Impossibility to obtain 3 measures of TOF ratio at PACU;

If a patient withdraws from the study for any reason before its completion, the reason and the date of withdrawal should be recorded on the CRF.

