# 7. STATISTICAL ANALYSIS

## 7.1. Sample size determination

Sample size determination was calculated by assuming that the Portuguese population to be submitted to elective surgery with general anesthesia is approximately 100.000 cases/year.

From the previous study of [name] et al, the incidence of patients that arrive at the post anesthesia care unit with objective evidence of incomplete neuromuscular recovery was 26%.

When considering this incidence of 26%, a margin of error of 5% (acceptable maximum deviation) and a confidence interval of 95%, we obtained a minimum sample size of 295 patients (StatsDirect 3 Statistical Software).

Considering conservative estimation for the discontinuation rate of 20%, it is expected that approximately 360 patients are required to achieve the primary endpoint.

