## 7.7. Statistical and Analytical Methods

### 7.6.1. Definition of Analysis Population

Full analysis set population (FAS) will include all treated patient if the patient meets the all criteria.

TOF result will be defined as the average of 3 measures. If the 3 measures have a difference above 20%, another sequence of 3 TOF measurements should be assessed.

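### Patients removed at the PACU leave before the only scheduled adverse-event and outcome collection, so the safety frequencies describe TOF-evaluable patients only

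*Combined protocol and SAP*

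**What the plan says.** A subject is enrolled on giving written consent (section 6.2), which happens at the preoperative visit, and must receive a non-depolarizing NMBA during surgery (section 6.4.1). Three rules can then remove that patient at the PACU:

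- Section 6.4.3: "Additionally subject participation must be terminated during the study for any of the following reasons", the reason listed being "Impossibility to obtain 3 measures of TOF ratio at PACU".
- Section 6.3.1, neuromuscular blockade evaluation: if the measurements in the second sequence "still differ more than 20% between the maximum and the minimum the patient will be excluded".
- Section 6.4.2: exclusion if "More than 10 minutes elapsed between extubation and neuromuscular block monitoring at PACU".

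The flow chart (section 1.1) marks adverse events and final outcome in one column only, "At hospital discharge", and section 6.3.2 places their recording in Period 2. For a patient who withdraws, section 6.4.3 asks for the reason and date.

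The only analysis set is in section 7.6.1: "Full analysis set population (FAS) will include all treated patient if the patient meets the all criteria". The statistical methods text in section 7.6.2 likewise admits subjects who meet the study criteria. Adverse events and final outcome are listed variables there, and no other population is defined for them.

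Section 8 adds a separate route: SAEs go to the sponsor within 24 hours of awareness, and non-serious events are recorded in the CRF with no time point given.

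**The concern.** The three removal rules concern whether the TOF reading is usable. That is a reason to leave a patient out of the TOF incidence, but not a reason to stop recording what happens to a consented patient who has already been exposed to the blocker. As written, the rules do both. The patient leaves before the scheduled safety record is made, and no text continues AE or outcome collection afterwards.

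The AE, SAE and death frequencies would then apply to patients who met the PACU timing and TOF criteria, without the report saying so. The rationale (section 4) names hypoxemia, aspiration risk and impaired airway reflexes as consequences of residual blockade, so a reader will look for these events. If removal is related to such events, the frequencies mislead. If it is not, some exposed patients still have no recorded outcome.

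**Working it through.** **1. Sequence of events.** Consent, NMBA exposure, PACU arrival and possible removal, then discharge with AE and outcome recording. Each removal rule acts before the recording step. The flow chart also marks dates of discharge or death under PACU arrival, but these cannot be known then, so that row supplies no earlier outcome record.

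**2. Who is outside the analysis set.** Patients excluded for variability or timing do not meet the criteria, so they are outside the FAS. For patients terminated under section 6.4.3 this is the natural reading but not an explicit one: the FAS wording does not say whether discontinuation criteria count. Section 6.2 does class these patients as discontinued.

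**3. What section 8 covers.** The 24-hour SAE duty is not tied to the discharge visit. It does not say whether the duty persists after removal, and it creates no population in which those SAEs would be tabulated.

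**4. The plan's own figures (section 7.1).** Inputs: incidence 26%, margin 5%, 95% confidence, population 100,000.

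- n0 = 1.96² × 0.26 × 0.74 / 0.05² = 295.6
- With finite population correction: 295.6 / (1 + 294.6/100,000) = 294.8, so 295, as stated.
- Allowing for 20% loss: 295 / 0.80 = 369, or 295 × 1.20 = 354. The stated total of approximately 360 lies between the two.
- 20% of 360 = 72 patients, leaving 288.

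The 72 is a ceiling for removals within that allowance. The 20% is described as conservative and covers discontinuation in general, including voluntary withdrawal. The plan does not say whether timing exclusions under section 6.4.2 are counted in it.

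**5. Effect on recorded AE risk.** The documents give no AE rate and no comparison of removed with retained patients, so both are assumptions here. Let f be the share removed and RR the AE risk in removed relative to retained patients. If removed patients contribute neither events nor denominator,

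recorded risk / true risk = 1 / ((1 − f) + f × RR).

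| Share removed | RR 0.5 | RR 1 | RR 2 | RR 3 |
|---|---|---|---|---|
| 5% (18 of 360) | 1.03 | 1.00 | 0.95 | 0.91 |
| 10% (36 of 360) | 1.05 | 1.00 | 0.91 | 0.83 |
| 20% (72 of 360) | 1.11 | 1.00 | 0.83 | 0.71 |

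Worked cell, f = 20% and RR = 2: 1 / (0.80 + 0.40) = 0.83. In absolute terms, with an assumed 3% risk in the 288 retained and 6% in the 72 removed, the true risk is (8.64 + 4.32) / 360 = 3.6%, against 3.0% recorded.

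**The case against.** The strongest case on the other side has four parts.

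*Serious events have their own route.* Section 8 requires SAEs within 24 hours of awareness, whatever the visit schedule. This stands, and it means discharge is the only scheduled collection point rather than the only possible one. It would be wrong to infer that serious events in removed patients must disappear. What is open is whether the duty continues after removal and where such events are reported.

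*Removal need not reflect the patient's condition.* A reader might infer that unstable patients are the ones who miss the measurement. The text does not establish this. The measurement is to be made "as soon as clinically adequate (basic monitoring and oxygen therapy in place"), which describes a set-up condition. Section 6.5 allows up to a 10-minute walk from OR to PACU, so transport alone can use up the 10-minute limit, and section 6.4.3 gives no cause for failed measurement. A patient who needs stabilising on arrival could also exceed the limit, so clinical selection remains possible. The plan cannot distinguish the two unless removed patients are followed and reported by reason.

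*The direction of bias is not established.* This stands. At equal risk there is no bias, and at a lower risk in removed patients the recorded rate is too high.

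*Safety is not an endpoint.* Adverse events appear in no primary, secondary or exploratory objective, are summarised descriptively, and no treatment is assigned. This limits the importance of the point but does not remove it, because the plan does list AEs and final outcome as variables to be reported.

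**Conclusion.** The point holds as a gap in safety follow-up and reporting. Under the rules as written, consented and exposed patients can leave the study before the scheduled AE and outcome record, and the descriptive frequencies are conditional on TOF evaluability. This is firm for variability and timing exclusions. For terminations under section 6.4.3 it rests on the natural reading of the FAS definition.

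A reader might go further and conclude that AE rates are biased low because only well patients are measured. The documents do not support that as a fact: it requires a higher AE risk in removed patients, which is plausible but not shown. The size cannot be derived from the plan. The table's range, from 0.71 to 1.11 of the true risk, depends on assumed risk ratios of 0.5 to 3 and on removal of 5% to 20%, the upper figure being a ceiling.

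The primary incidence and the association analyses are not affected by this point. It is a worthwhile, low-cost correction rather than a threat to the study's main result.

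**What to change.** 1. In sections 6.4.2 and 6.4.3 and in the TOF evaluation text of section 6.3.1, state that failing a TOF or timing criterion removes the patient from the TOF analysis only, and that AEs, SAEs and final outcome are still collected to discharge unless consent is withdrawn.
2. In section 8, confirm that SAE reporting continues for these patients.
3. In section 7.6.1, add that AEs, SAEs and deaths are reported descriptively for all consented patients who received a non-depolarizing NMBA, split by TOF-evaluable or not, with the reason for each removal.

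The cost is protocol wording, discharge data entry for at most about 72 patients on the plan's own 20% allowance, and one extra table. Consent under section 9.1.1 already covers data that become available in routine care, and no extra visit is needed. The TOF analysis set and the sample size do not change.
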